9.5.2.3 Modified Fatigue Impact Scale (MFIS)

The MFIS, which has been shown to be a useful clinical outcome measure for subjects with FA [Epstein et al, 2008; Friedman et al, 2010], will be completed by all subjects or their caregivers at Baseline/Day 1 (Week 26 of Study HZNP-ACT-301) and at Weeks 13 and 26 (or PW). The MFIS is a 21-item assessment, with each item rated on a 5-point scale (0=never \rightarrow 4=almost always) (Section 17.7). It can be aggregated into three subscales (physical, cognitive, and psychosocial), as well as into a total MFIS score. All items are scaled so that higher scores indicate a greater impact of fatigue on a subject's activities (i.e., no items are reverse scored).

9.5.3 Safety Variables

Safety will be assessed via AE and concomitant medication use monitoring, immunogenicity testing, physical examinations, vital signs, clinical safety laboratory evaluations (complete blood count, PT, INR, aPTT, chemistry, and urinalysis), pregnancy testing (if applicable), echocardiograms, and ECGs.

9.5.3.1 Adverse Events

Comprehensive assessments of any apparent AE experienced by the subject will be performed throughout the course of this study. Study center personnel will record all AEs, whether observed by the Investigator/designee or reported by the subject/caregiver, in the source document and on the eCRF. A physician (either the Principal Investigator or a physician/nurse practitioner/physician's assistant designated by the Principal Investigator) will manage and treat any treatment-emergent AE (TEAE).

AE information will be elicited from each subject/caregiver by indirect questioning using a non-leading question, such as "Has anything bothered you since your last visit or is anything bothering you now?" AE data also may be volunteered by the parent/caregiver to the Investigator (or designee). A physician (either the Principal Investigator or a physician/nurse practitioner/physician's assistant designated by the Principal Investigator) will assess the seriousness, severity, and causality of each AE based on the following definitions and documentation requirements.

9.5.3.1.1 Definitions

Adverse Event: An AE is defined in 21 CFR 312.32(a) as any untoward medical occurrence associated with the use of a drug in humans, whether or not considered drug-related.

A TEAE is any adverse change from the subject's baseline condition, including any laboratory test value abnormality judged as clinically significant by the investigator, that occurs on or after the date of the first dose of study drug administered at home and throughout the duration of the clinical study, whether the AE is considered related to the treatment or not. Adverse events include the following types of occurrences:

- Adverse reaction: an adverse reaction means any AE caused by a drug. Adverse reactions are a subset of all suspected adverse events for which there is reason to conclude that the drug caused the event.
- Suspected adverse reaction means any AE for which there is a reasonable possibility that the drug caused the AE. Reasonable possibility means there is evidence to suggest a causal relationship between the drug and the AE. A suspected adverse reaction implies a lesser degree of certainty about causality than adverse reaction, which means any AE caused by a drug. Suspected adverse reactions are the subset of all AEs for which there is a reasonable possibility that the drug caused the event.
- Other medical experiences, regardless of their relationship to the study drug, such as injury, accidents, increased severity of pre-existing symptoms, apparently unrelated illness, and clinically significant abnormalities in clinical laboratory values, physiological testing, or physical examination findings.
- Reactions from drug overdose, abuse, withdrawal, sensitivity, an interaction with another drug or substance, or toxicity.

Serious Adverse Event (SAE): An AE is considered serious if, in the view of either the Investigator or Sponsor, it results in any of the following outcomes:

- Death. This includes any death that occurs during the conduct of a clinical study, including deaths that appear to be completely unrelated to the study drug (e.g., car accidents).
- Life-threatening adverse experience. An AE or suspected adverse reaction is considered life-threatening if, in the view of either the Investigator or the Sponsor, its occurrence places the subject at immediate risk of death. It does not include an AE or suspected adverse reaction that, had it occurred in a more severe form, might have caused death.
- Persistent or significant disability or incapacity.
- Inpatient hospitalization or prolongation of an existing hospitalization.

- Congenital anomaly or birth defect.
- Other medically important event which, according to appropriate medical judgment, may require medical or surgical intervention to prevent one of the outcomes listed above.

Of note: Surgical procedures or other therapeutic interventions themselves are not adverse events, but the condition for which the surgery/intervention is required is an adverse event and should be documented accordingly.

Elective surgeries and/or treatments requiring hospitalization (e.g., cosmetic surgery), and treatment received at an emergency room or similar facility, will not be considered as SAEs unless one of the definitions of an SAE listed above is met.

Non-Serious Adverse Event: A non-serious AE includes any AE that is not described in the previous SAE category.

Unexpected: An AE or suspected adverse reaction is considered unexpected if it is not listed in the Investigator Brochure or is not listed with the specificity or severity that has been observed. Unexpected, as used in this definition, also refers to AEs or suspected adverse reactions that are mentioned in the Investigator Brochure as occurring with a class of drugs or as anticipated from the pharmacological properties of the drug, but are not specifically mentioned as occurring with the particular drug under investigation.

9.5.3.1.2 Documentation of Adverse Events

Adverse events that are ongoing from Study HZNP-ACT-301 will be considered baseline signs/symptoms. The TEAE reporting period begins with the date of the first dose of study drug at home and continues until completion of the Follow-Up Safety Visit, performed two weeks after administration of the final dose of study medication. All baseline signs/symptoms and TEAEs must be recorded in the source documents and on the subject's eCRF.

If the Investigator observes an SAE after study completion that he/she believes was possibly caused by the study medication, the Investigator will report this SAE using the procedures described in [Section 9.5.3.1.5](#).

Unchanged, chronic conditions are **NOT** considered AEs and should not be recorded on the AE pages of the eCRF unless there is an exacerbation of a chronic condition.

Disease progression can be considered as a worsening of a subject's condition attributable to the disease for which the study drug is being studied (i.e., FA). It may be an increase in the severity of the disease under study and/or increases in the symptoms of the disease. The development of worsening ataxia may be considered as disease progression and not an AE. Events, which are unequivocally due to disease progression, should only be reported as AEs if they fulfill any of the SAE criteria or are the reason for discontinuation of treatment with the study drug.

In addition, hospitalizations for planned procedures are not considered an AE unless they are prolonged hospitalizations, and emergency room visits less than 24 hours in duration are not considered hospitalizations.

Detailed information regarding all SAEs must also be recorded on the Serious Adverse Event Reporting Form. Whenever possible, the Investigator should group together into a single term the signs and symptoms that constitute a single diagnosis. For example, cough, rhinitis, and sneezing might be grouped together as “upper respiratory infection” if the Investigator is confident of the diagnosis.

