- ¹⁰ The PedsQL (study subject and parent/caregiver assessments) will be administered throughout the study for subjects who received the PedsQL at their Baseline Visit of the HZNP-ACT-301 study (even if subjects turn 18 during their participation in either Study HZNP-ACT-301 or HZNP-ACT-302). The SF-36 will continue to be administered throughout the study for subjects who completed the SF-36 during their HZNP-ACT-301 study participation.
- ¹¹ Adverse events occurring or worsening on or after the date of administration of the first dose of study drug at home through the end of the study will be considered treatment-emergent adverse events (TEAEs). All SAEs that occur on or after the date of administration of the first dose of study drug at home through two weeks after study discontinuation will be recorded.
- ¹² If a subject tests positive for anti-drug antibodies (ADA), he/she will be followed until ADA levels revert to baseline.
- ¹³ Brief physical examinations will be performed at the Week 4 and Follow-Up Safety Visits; all other examinations will be complete physical examinations.
- ¹⁴ Only for female subjects of childbearing potential.
- ¹⁵ Collect blood samples for clinical safety laboratory testing (9.3 mL; 1.0 mL for hematology, 3.5 mL for chemistry, 3.0 mL discard, and 1.8 mL for PT/INR/aPTT) and a urine sample for urinalysis.

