9.5.3.1.5 Reporting and Documenting SAEs

All SAEs beginning with the time of signing IC and continuing until two weeks after administration of the final dose of study medication must be reported. The following steps will be taken to report promptly and document accurately any SAE, whether or not it appears to be related to the study medication:

- 1) Report the SAE to Med Communications, Inc. **by telephone or fax within 24 hours** after becoming aware that a subject has experienced an SAE (see [Appendix 17.1](#) for contact information).
- 2) Record the SAE accurately in the source documents and on the AE page of the subject's eCRF, as described in [Section 9.5.3.1.2](#). Using the Serious Adverse Event Reporting Form, submit all known subject information to Med Communications, Inc. (as specified in separate instructions provided to the study center) on the SAE reporting form **within 24 hours of learning of the SAE occurrence**.

- 3) Perform appropriate diagnostic tests and therapeutic measures, and submit all follow-up substantiating data, such as diagnostic test reports, hospital discharge summaries, and autopsy report to the Sponsor's representative.
- 4) Respond in a timely manner to any queries from Sponsor regarding the SAE.
- 5) Conduct appropriate consultation and follow-up evaluation until the SAE is resolved, stabilized, or otherwise explained by the Investigator.
- 6) Review each SAE report and evaluate the relationship of the SAE to study treatment. The Sponsor will determine whether the SAE is unexpected in nature.
- 7) The Investigator must report all AEs or SAEs that meet the criteria for Unanticipated Problems Involving Risks to Human Subjects or Others to the IRB.

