6.3 Derived and Computed Variables

The following derived and computed variables have been initially identified as important for the analyses of Safety, Efficacy and Exploratory endpoints. It is expected that additional variables may be required. The SAP will not be amended for additional variables that are not related to the primary target or key secondary target variables. Any additional derived or computed variables will be identified and documented in the SAS programs that create the analysis files. If the SAP is not amended, further derivations related to primary and secondary target variables will be described in the CSR.

- 302 Baseline = The last non-missing measurement/assessment on the date of Week 26 Visit from HZNP-ACT-301. If this measurement is missing or otherwise unavailable, it will be the last non-missing measurement/assessment on or prior to first dose in HZNP-

ACT-302.

- 301 Baseline = The last non-missing measurement/assessment prior to first dose of Study in HZNP-ACT-301.
- Study Day = Assessment Date – Date of Enrollment + 1
- Change from Baseline = Value at Post-Baseline – Value at Baseline
- Concomitant Medication is defined as any medication a subject has received concurrently with study treatment.
- Prior Medication is defined as any medication or therapies initiated prior to date of first dose of study drug. Medications that are started prior to the date of first dose of study drug and continue after the first dose of drug are considered to be both prior and concomitant medications.
- Treatment-Emergent Adverse Event (TEAE) – A TEAE is any adverse change from the subject's baseline condition that occurs on or after the date of the first dose of study drug through the duration of the clinical study.
- Related TEAE – Any TEAE with a reported relationship to study drug of 'possibly related'.
- Compliance = Calculated as the percentage of the number of vials used divided by the expected number of vials used, where the number of vials used is the number of used vials returned.

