9.6 Exposure and Compliance

For each subject, treatment compliance and exposure will be calculated and summarized for the entire study. Overall compliance and exposure will be summarized and grouped by overall treatment. Compliance is defined in Section 6.3. Drug accountability, exposure, and treatment compliance will also be provided in a subject listing.

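### Reactions that began on ACTIMMUNE in 301 and continue unchanged are not TEAEs in 302, and the legible SAP text describes no safety summary spanning both studies

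*Protocol*

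**What the plan says.** **Events carried over from 301.** Protocol 9.5.3.1.2: "Adverse events that are ongoing from Study HZNP-ACT-301 will be considered baseline signs/symptoms". The rule does not distinguish subjects who had ACTIMMUNE in 301 from those who had placebo. The same section adds "The TEAE reporting period begins with the date of the first dose of study drug at home", and on recording: "All baseline signs/symptoms and TEAEs must be recorded in the source documents and on the subject's eCRF". It also keeps unchanged chronic conditions off the AE pages.

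**TEAE definition.** Protocol 9.5.3.1.1 defines a TEAE as an adverse change relative to baseline, with this timing: "that occurs on or after the date of the first dose of study drug administered at home and throughout the duration of the clinical study". SAP 6.3 has the same idea: an adverse change from baseline "that occurs on or after the date of the first dose of study drug through the duration of the clinical study". Footnote 11 to the schedule in Protocol 2.1, repeated under Table 2 of the SAP, is more explicit: "Adverse events occurring or worsening on or after the date of administration of the first dose of study drug at home". SAP 6.3 does not mention worsening, and it does not say that the first dose meant is the home dose.

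**Tables.** SAP 9.1 tabulates TEAEs by system organ class and preferred term, by relationship and by severity. Events that are not treatment-emergent appear in the listings with a flag. SAP 2.2.1 measures laboratory, vital-sign, ECG and echocardiogram changes from the 302 Baseline. SAP 9.6 says that "treatment compliance and exposure will be calculated and summarized for the entire study", with no start date, stop date or formula.

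**Objective.** Long-term safety is the primary objective (Protocol 8.1, SAP 2.1.1). The 52-week summaries in Protocol 9.6.1 were for efficacy only, and SAP 2.2, 8 and 10 remove all efficacy analysis.

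**The concern.** For a subject who had placebo in 301, an event ongoing at Day 1 of 302 is a true pre-treatment condition. For a subject who had ACTIMMUNE, the same entry may be a reaction to the drug under study, because the 302 baseline is that subject's Week 26 on active treatment. The rule treats the two alike.

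Reactions that persist are among the things that long exposure should reveal. When they continue unchanged they are left out of the 302 TEAE tables, and nothing in the legible SAP text puts them back in an overall account of these subjects' exposure. Safety is now the only analysis left in the SAP, so the gap falls on the study's one remaining purpose. The omission can only lower the TEAE counts.

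A related gap makes this harder to see. The protocol synopsis promises every summary by 301 treatment and overall. SAP 6 says only that summaries are by overall treatment, and SAP 10 does not list this as a change. If that wording means one pooled column, subjects with 26 and 52 planned weeks on drug are combined.

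**Working it through.** **1. The plan's own figure.** 26 weeks of blinded treatment in 301 (Protocol 9.3.1) + 26 weeks in 302 (synopsis) = 52 weeks. This reproduces the 52-week duration stated in Protocol 9.6.1. The visit days agree: 26 × 7 + 1 = 183 and 28 × 7 + 1 = 197.

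**2. Share of follow-up that the TEAE tables cover, for subjects active in both studies.**
- 302 TEAE window with the two-week follow-up: 26 + 2 = 28 weeks.
- First 301 dose to the 302 follow-up visit: 26 + 26 + 2 = 54 weeks.
- With follow-up: 28/54 = 52%. On treatment only: 26/52 = 50%.

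**3. What happens to an event that began on ACTIMMUNE in 301 and is present at Day 1.**

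| Course in 302 | 302 TEAE? | Basis |
|---|---|---|
| Continues unchanged | No | Protocol 9.5.3.1.2 with 9.5.3.1.1 |
| Worsens | Yes under the protocol; SAP 6.3 does not say so expressly | Protocol 2.1, footnote 11; SAP 6.3 |
| Resolves, then recurs | A new occurrence on a plain reading | Protocol 2.1, footnote 11 |
| Eases without resolving, then returns to its earlier grade | Not settled | No section addresses it |

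Only the first row is clearly excluded.

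**4. What stays visible.** The event is recorded on the eCRF and may reach the flagged listing, which gives no incidence. SAP 9.2 tabulates absolute laboratory values and counts below, within and above the normal range at each visit. A persistently abnormal laboratory value therefore remains visible even though its change from the 302 Baseline is near zero. SAP 9.3 and 9.4 likewise give absolute vital-sign and ECG values. The gap is mainly in clinical adverse events.

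**5. Illustration only.** The documents give no 26-week event rates for Friedreich's ataxia. Assume an incidence p in each 26-week half with constant hazard. Let s be the share of 301-onset events that persist unchanged. Assume also that a subject with such an event has no new or worse event of the same term in 302.
- 52-week cumulative incidence = 1 − (1 − p)².
- Incidence in a 302-only TEAE table = p(1 − p·s).

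| p | 52-week cumulative | 302 table, s = 0 | s = 0.5 | s = 1 |
|---|---|---|---|---|
| 5% | 9.8% | 5% | 4.9% | 4.8% |
| 10% | 19% | 10% | 9.5% | 9% |
| 20% | 36% | 20% | 18% | 16% |
| 40% | 64% | 40% | 32% | 24% |

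Under these assumptions the missing cumulative summary accounts for more of the difference than the carry-over rule itself. Protocol 7.3 says that tolerance to flu-like symptoms develops quickly, so a constant hazard is doubtful for those events.

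**The case against.** The strongest reply is that judging emergence against the extension's own baseline is a defensible choice, that nothing is lost from the record, and that an integrated 301 and 302 analysis may be planned elsewhere. All three stand as far as they go. The first is a reason to leave the 302 definition alone. The second shows that the gap is in tabulation, not in collection. The third cannot be excluded, because the list of planned tables is unreadable and other reports were not available.

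A reader might infer more than the documents support:

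- **That every AE and exposure window restarts at the first home dose.** Protocol 9.5.3.1.5 requires reporting of "All SAEs beginning with the time of signing IC and continuing until two weeks after administration of the final dose of study medication", so SAE reporting starts at consent there. This conflicts with footnote 11 of the schedule, which starts at the first home dose. The exposure window in SAP 9.6 is undefined rather than shown to restart, and Study Day in SAP 6.3 counts from enrollment.
- **That an event which eases and returns is never a TEAE.** No section says so, and footnote 11 counts events that occur or worsen after the first home dose.
- **That the understatement can be sized from the label's 52% fever rate.** That rate is from chronic granulomatous disease at 50 mcg/m², in a trial with mean treatment of 8.9 months. The share of events still ongoing at Day 1 would have to be invented.
- **That continuing subjects will be shown as tolerating the drug better than switchers because of relabelling.** This needs output by 301 arm, which the SAP does not clearly provide. Tolerance and the selection of 301 completers could produce the same pattern.
- **That the remedy is a different 302 TEAE rule for each former arm.** That would make TEAE rates non-comparable between the arms and would count the same event in both studies.

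**Conclusion.** The point holds for events that began on ACTIMMUNE in 301 and continue unchanged. They are absent from the 302 TEAE incidence, severity and relatedness tables, and the legible SAP text describes no safety summary across the two studies. For subjects active in both studies the TEAE tables cover 28 of 54 weeks, or 26 of 52 on treatment. The primary objective of long-term safety is therefore only partly served for the subjects with the longest exposure.

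The direction, lower TEAE counts, follows from the rule. Its size does not follow from the documents: it depends on how many events are ongoing and unchanged at Day 1, which they do not give. The conclusion assumes that the unreadable table list holds no cumulative safety table. This is a worthwhile, inexpensive improvement to the reporting, not a flaw in data collection.

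**What to change.** Keep the 302 TEAE definition in its present scope for both former arms, and keep site recording as it is. Then:

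1. In SAP 9.1, add a table by 301 arm of adverse events ongoing at 302 entry, with onset, severity, relationship, duration and outcome.
2. In SAP 9.1 and 9.6, add a cumulative TEAE and exposure table for subjects on ACTIMMUNE in both studies, from the first 301 dose to the 302 follow-up visit, judged against the 301 Baseline that SAP 6.3 already defines. Count each subject once per preferred term, and state that the table is not to be added to the 301 or 302 tables.
3. In SAP 9.6, define the start and stop of exposure.
4. In SAP 6.3, add worsening and the home dose to the TEAE definition, to match footnote 11.
5. Reconcile the start of SAE recording between Protocol 9.5.3.1.5 and footnote 11 in both documents.
6. State in SAP 6 whether summaries are split by 301 treatment, as the synopsis promises. If they are not, record that in SAP 10.

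The cost is two or three more tables from 301 adverse-event and dosing data that the sponsor should already hold. 301 must be locked and unblinded first, which the synopsis's split by 301 treatment already requires. Reported incidence in continuing subjects will rise, because the cumulative table covers a longer period and includes events that began in 301.

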9.5.3.1.3 Grading of Adverse Events

The severity of all AEs, including all treatment-emergent clinically significant laboratory test results and all treatment-emergent clinically significant changes in laboratory test results, will be assessed in accordance with the following criteria:

- Mild (Grade 1): awareness of signs or symptoms that are easily tolerated, are of minor irritant type, cause no loss of time from usual activities, do not require medication or further medical evaluation, and/or are transient.
- Moderate (Grade 2): signs or symptoms sufficient to interfere with function but not activities of daily living.
- Severe (Grade 3): signs or symptoms sufficient to interfere with activities of daily living; signs and symptoms may be of a systemic nature or may require further medical evaluation and/or treatment.
- Life-Threatening (Grade 4): disabling or with life-threatening consequences. This definition does not include any event that might have caused death if it had occurred in a more severe form.
- Fatal (Grade 5): death related to an AE.

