5.3 Bone Marrow Toxicity

Reversible neutropenia and thrombocytopenia that can be severe and may be dose related have been observed during ACTIMMUNE therapy. Monitor neutrophil and platelet counts in patients with myelosuppression during treatment with ACTIMMUNE.

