5.4 Hepatic Toxicity

Repeated administration of ACTIMMUNE to patients with advanced hepatic disease may result in accumulation of interferon gamma-1b. Frequent assessment of liver function in these patients is recommended.

Elevations of aspartate transaminase (AST) and /or alanine transaminase (ALT) (up to 25-fold) have been observed during ACTIMMUNE therapy. The incidence appeared to be higher in patients less than 1 year of age compared to older children. The transaminase elevations were reversible with reduction in dosage or interruption of ACTIMMUNE treatment. Patients begun on ACTIMMUNE before age one year should receive monthly assessments of liver function. If severe hepatic enzyme elevations develop, ACTIMMUNE dosage should be modified [see *Dosage and Administration (2.3)*].

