9.1 Adverse Events

Missing and partially missing AE start and/or stop dates will be imputed for the purpose of statistical analysis, according to the specifications described in Section 6.1.

A summary of overall TEAEs, TEAEs, SAEs, TEAEs leading to PW, TEAEs by relationship to study drug, and severity of TEAEs will be presented by overall treatment.

Summaries and incidence rates (frequencies and percentages) of individual TEAEs by MedDRA System Organ Class (SOC) and preferred term will be displayed by overall treatment received. Such summaries will be displayed for TEAEs, SAEs, TEAEs leading to early termination, TEAEs by relationship to study drug, and TEAEs by severity

Each subject will be counted only once within each preferred term. If a subject experiences more than one TEAE within a preferred term only the TEAE with the strongest relationship or the maximum intensity, as appropriate, will be included in the summaries of relationship and intensity. No inferential statistical tests will be performed.

In the AE data listings, all AEs will be displayed. AEs that are not treatment-emergent will be flagged.

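### Protocol 9.5.3.1.3 grades laboratory adverse events on symptoms and function with no value-based criterion, so the severity table does not reliably show the size of laboratory toxicity

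*Protocol*

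**What the plan says.** Protocol 9.5.3.1.3 begins "The severity of all AEs, including all treatment-emergent clinically significant laboratory test results" and extends the same rule to significant changes in laboratory results. Five grades follow.

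- Mild covers events that are easily tolerated, cost no time from usual activities, and "do not require medication or further medical evaluation, and/or are transient".
- Moderate is "signs or symptoms sufficient to interfere with function but not activities of daily living".
- Severe leads with "signs or symptoms sufficient to interfere with activities of daily living". A second clause adds that these may be systemic, or may call for more work-up or therapy.
- Grade 4 rests on disability or danger to life as the consequence.
- Grade 5 is death.

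The labeling reproduced in Protocol 17.2 applies the word severe to the laboratory finding itself. Its section 5.4 says "If severe hepatic enzyme elevations develop, ACTIMMUNE dosage should be modified", and its section 5.3 says "Reversible neutropenia and thrombocytopenia that can be severe and may be dose related have been observed during ACTIMMUNE therapy".

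On reporting, SAP 9.1 states that "TEAEs by relationship to study drug, and severity of TEAEs will be presented by overall treatment". SAP 9.2 adds three laboratory outputs: by-visit summaries of values and changes from baseline, shift tables in three categories (low, normal, high), and listings that flag out-of-range results.

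**The concern.** Laboratory toxicity is usually silent when it is found, and its severity is then a matter of how far the value has moved. A scale built on symptoms and function measures something else. If the grade does not move with the size of the abnormality, a severity table built from it cannot tell a marginal rise from a marked one.

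That matters more here than in most extension studies. Long-term safety is the primary objective (Protocol 8.1). The target dose is 100 µg/m² against a labeled 50 µg/m², a factor of 100/50 = 2 (Protocol 7.3, Table 7.1), and Protocol 9.2 says the safety profile of that dose in children with this disease is not known. SAP 2.2 and SAP 8 drop all efficacy analysis, so the study report rests on the safety tables. The protocol's own example of a drug-related event after Week 13 is raised liver tests (9.4.1.1), and Protocol 7.3 describes a transaminase elevation in the pilot study.

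**Working it through.** There is no figure to reproduce and no arithmetic beyond the dose ratio. The check is to apply the grading text to one event and then see what each planned output would show.

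**The event.** A transaminase, neutrophil or platelet abnormality that causes no symptoms and that the investigator judges clinically significant. That judgement is what makes it a treatment-emergent event under Protocol 9.5.3.1.1, which gives no numeric threshold. If the result is unexplained, Protocol 9.5.3.1.6 requires prompt repeat testing and follow-up, which is further evaluation.

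**The grades.**

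| Grade | What the text turns on | Does the event fit? |
|---|---|---|
| 1 | Easily tolerated; no work-up needed, and/or transient | Against: it needs repeat testing. For: it may be transient, and the two are joined by and/or |
| 2 | Interference with function | No: nothing is interfered with |
| 3, lead clause | Interference with daily living | No |
| 3, second clause | May need work-up or therapy | Yes, but only if this clause is read as sufficient by itself |
| 4 | Disabling or life-threatening consequence | Only if the investigator judges the consequence so; no symptom wording and no value |

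**The readings.**

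- If the lead clause of Grade 3 is required, every silent abnormality falls nearest to Grade 1, whatever its size.
- If the need for work-up is enough, every unexplained significant abnormality can be called Grade 3, whatever its size, because 9.5.3.1.6 requires work-up for all of them.
- Grade 4 depends on individual judgement with no threshold.

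Under neither of the first two readings does the grade follow the size of the abnormality, and across all three the same event can be Grade 1, 3 or 4.

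**The other outputs.**

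- *Shift tables (SAP 9.2).* A value at 1.1 times the upper limit and one at 25 times the upper limit both count as high.
- *By-visit summaries (SAP 6 and 9.2).* The minimum and maximum are given. If the maximum among n subjects passes some marked level, the number of subjects beyond that level could be anything from 1 to n. The mean, median and SD narrow this but do not give the count.
- *Unscheduled results (SAP 6).* These are listed and not summarized. Scheduled laboratory visits after baseline fall on Days 29, 92 and 183 (Protocol 2.1), so a peak caught between them appears only in a listing.
- *Repeat results (SAP 6.2).* These are not used unless the original is missing or invalid.
- *Missing severity (SAP 6.2).* This is imputed as Severe, which pushes the table upward but does nothing for events that carry a recorded grade.

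No planned table therefore gives the number of subjects with a marked laboratory abnormality.

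**The case against.** A reader might go further and infer that a silent laboratory abnormality can never be Grade 3, that the severity table is biased downward, and that sites would never treat such an event as severe when adjusting dose. The documents do not support any of these.

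- Grade 3 has its second clause, and Grade 4 has no symptom wording. Because the section expressly brings laboratory results onto the scale, an investigator could reasonably read signs to include them. The text is ambiguous; it does not close off the higher grades.
- Nothing shows which reading sites would choose. Understatement is possible, not established, and the imputation of missing severity works the other way.
- Protocol 9.4.1.1 leaves severe reactions during escalation to the investigator's judgement and does not refer to 9.5.3.1.3. After Week 13 it allows reductions for drug-related events with no grade required. The two sections use one word without saying whether it means the same thing, which is a gap and not a contradiction.

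The label's most striking figures also need care. Section 6.2 of the label itemizes the 2- to 25-fold transaminase rises in 6 of 10 patients treated before age one year, and the neutrophil count of 525 cells/mm³ comes from the same paragraph. Subjects here were 10 to 25 years old at the start of the parent study. Section 5.4 of the label gives the 25-fold figure without an age limit but says incidence appeared higher under one year. The argument does not depend on these figures.

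Finally, size is not invisible. Minimum, maximum, change from baseline and flagged listings would show an extreme value. Serious events and withdrawals due to adverse events are reported separately, and a safety board monitors the study. All of this stands. It limits the consequence, but it does not supply a count of subjects by size of abnormality or make the severity grade reproducible.

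**Conclusion.** The scale applies symptom and function criteria to laboratory events and offers no value-based criterion. The grade of an asymptomatic abnormality is therefore left to the reader, and the severity table should not be relied on to describe the size of laboratory toxicity. It may understate that toxicity; the direction is not established.

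The potential reach is every silent hepatic or hematologic adverse event. How many subjects that means cannot be derived from the documents. The study is descriptive and its sample size has no statistical basis (SAP 5.1), so no error rate or power is affected. What suffers is the primary safety description.

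The conclusion assumes that sites receive no separate value-based grading instructions; none appear in the protocol or SAP. The change is worth making because it is cheap and the data needed are already collected.

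**What to change.** 1. In Protocol 9.5.3.1.3, limit the symptom and function criteria to clinical events. Grade laboratory events by the size of the abnormality on one named published laboratory toxicity scale, chosen by the sponsor.
2. In SAP 9.2, add a table of the worst post-baseline grade per subject for each analyte on the scale, derived from central laboratory values and including unscheduled and repeat results. Show it separately from the investigator-graded table in SAP 9.1, so that two kinds of grade are not mixed and no rule is needed to link each event to a value. State whether grades refer to the laboratory's limits or to the subject's baseline; for subjects from the active arm, the baseline in SAP 6.3 is normally an on-treatment value.
3. Reconcile what severe means in Protocol 9.4.1.1 with 9.5.3.1.3. No dose rule is proposed here.

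The cost is a short protocol change, one derivation and one table, with no new samples. The small downside is the extra programming, and some laboratory events will carry a different, possibly higher, grade.
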